6.1.2 Statistical considerations

Cohort A (7-8/8 HLA-matched related or unrelated transplantation)

A 2-stage MiniMax design⁸⁶ will be used to test the null hypothesis that the progression-free survival rate is \leq 46% against the alternative hypothesis that it is \geq 71% in each arm. Nine patients will be treated in the first stage. If the number of patients who are alive without relapse/progression is equal to 4 or less at 1 year after transplantation in one arm, then the study for the arm will be terminated and the treatment is ineffective. If there are at least 5 patients (56%) who are alive without relapse/progression at 1 year after transplantation, the sample size will be increased up to a maximum of 25 patients. If the number of patients who are alive without relapse/progression is

equal to 15 or less at 1 year after transplantation, then the treatment is ineffective. If there are at least 16 patients (64%) who are alive without relapse/progression at 1 year after transplantation, this protocol will be deemed effective. This design has a significance level of 0.05, a power of 0.80, a probability of early termination under the null of 0.60, and an expected sample size under the null of 16 patients.

Table 4

Stage	Total Accrual	Close study/therapy if number of patients who are alive without relapse/progression is \leq
1	9	4 (44%)
2	25	15 (60%)

Cohort B (4-6/8 HLA-matched related transplantation)

A 2-stage MiniMax design will be used to test the null hypothesis that the progression-free survival rate is $\leq 34\%$ against the alternative hypothesis that it is $\geq 59\%$ in each arm. Twelve patients will be treated in the first stage. If the number of patients who are alive without relapse/progression is equal to 4 or less at 1 year after transplantation in one arm, then the study for the arm will be terminated and the treatment is ineffective. If there are at least 5 patients (42%) who are alive without relapse/progression at 1 year after transplantation, the sample size will be increased up to a maximum of 25 patients. If the number of patients who are alive without relapse/progression is equal to 12 or less at 1 year after transplantation, then the treatment is ineffective. If there are at least 13 patients (52%) who are alive without relapse/progression at 1 year after transplantation, this protocol will be deemed effective. This design has a significance level of 0.05, a power of 0.80, a probability of early termination under the null of 0.61, and an expected sample size under the null of 17 patients.

Table 5

Stage	Total Accrual	Close study/therapy if number of patients who are alive without relapse/progression is \leq
1	12	4 (33%)
2	25	12 (48%)

6.2 Primary Objective 3 and 4

3. To evaluate the rates of unacceptable toxicity of using NK cell-enriched DLI administered alone from a 7-8/8 HLA-matched related or unrelated donor or 4-6/8 HLA-matched related donor following allogeneic stem cell transplantation.
4. To evaluate the rates of unacceptable toxicity of using NK cell-enriched DLI administered with TLR9 ligand, DUK-CPG-001, from a 7-8/8 HLA-matched related or unrelated donor or 4-6/8 HLA-matched related donor following allogeneic stem cell transplantation.

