2.0 BACKGROUND

Myeloablative allogeneic stem cell transplantation may cure many types of diseases, but the toxicity associated with it limits its applicability. We and others have shown that reduced intensity/non-ablative therapy allows allogeneic therapy to be used by older, more infirmed patients with various types of neoplastic diseases and marrow failure syndromes.^{3,4,5,6} Our results have yielded nearly 100% donor engraftment with approximately a 10% death rate due to the procedure.⁷ Early response rates in the 75% range are encouraging in patients with minimal residual disease at the initiation of therapy, however long term remissions are still lacking. Earlier immune recovery may allow increased anti-tumor efficacy.⁸ Donor lymphocytes are one mechanism to assist earlier immune recovery and improved anti-tumor efficacy. However, the use of DLIs is limited by the risk of aGVHD. On the other hand, NK cells may mediate a GVT effect independently of aGVHD.

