
Thus, this study focuses on patients with only about a 50% chance of durable response from the allogeneic transplant at best, with infections and relapse being prime causes of morbidity and/or mortality. These data and others suggest that all patients post allogeneic transplant might be appropriate to consider an immunotherapy of some type except for the very good risk patients such as those with aplastic anemia, CLL or SLL or follicular lymphoma in first remission having needed only 1 regimen to attain a CR, or CML in first chronic phase entering in molecular remission without known molecular mutations.

2.3 Our program's Recent Preliminary Results Utilizing Fludarabine, Melphalan or Busulfan, and Alemtuzumab for Nonmyeloablative Therapy

We are currently conducting nonmyeloablative transplantation using fludarabine (160 mg/m²), melphalan (140 mg/m²), and alemtuzumab (80mg) for patients with lymphoid or myelomatous diseases, and fludarabine (160 mg/m²), busulfan (260 mg/m²), and alemtuzumab (80 mg) for patients with myeloid diseases.²⁷ Preliminary analysis of 98 patients showed that 1-year progression-free survival for 6/6 HLA-matched related or unrelated donor (n = 69) and 3-5/6 HLA-matched related donor (n = 29) was 46% and 34%, respectively. Although results are promising considering from high-risk disease status of enrolled patients, relapse and infection are the main causes of death, suggesting that strategy for enhancing graft-versus-tumor effects is required to further improve the outcomes of stem cell transplantations after nonmyeloablative conditioning.

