4.4 Patient NK cell infusion and CpG administration plan

This treatment regimen may be administered on an outpatient basis.

4.4.1 NK cell-enriched DLI:

The target cell dose for NK cell-enriched DLI will be as many cells as can be collected with less than 0.5×10^6 CD3+ CD56- cells/kg patient weight in the 4-6/8 HLA-matched related setting and 1×10^6 CD3+ CD56- cells/kg patient weight in the 7-8/8 HLA-matched related or unrelated setting. The first NK cell-enriched DLI will be administered between one to six months post-transplant. The second NK cell-enriched DLI will be administered one to three months post the first infusion, in patients who have < grade II aGVHD at the time of infusion and have not had unacceptable toxicities (see 6.2.1 Definition of unacceptable toxicity) that are at least possibly related to the previous DLI and resolved to grade 1 or less. The second DLI will NOT be administered in patient with \geq grade III aGVHD at the time of infusion or unacceptable toxicities at least possibly related to the first infusion. If patients have GVHD and were on immunosuppressive therapy at study entry, patients will continue on their stable dose of immunosuppressive agents started for therapy of acute GVHD before the NK cell-enriched DLI, and will not taper until at least 6 weeks following the each NK cell-enriched DLI (unless disease progression or patient toxicity from the agents requires earlier taper). The donor NK cells will be infused over 30 minutes. Diphenhydramine 25 mg iv or po, and Acetaminophen 650 mg po will be used prior to each reinfusion, unless there is a history of allergy or contraindication in the patient, in which case hydrocortisone 50mg IV will be used.

These cells are infused into the patient via a peripheral intravenous line or central line. If signs of GVHD occur after NK cell-enriched DLI, immunosuppressive agents (prednisone, cyclosporine, tacrolimus and/ or mycophenolate preferred first choices) may be started.

4.42 Adverse effect of NK cell-enriched DLI:

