6.2.2 Statistical considerations

Rate of unacceptable toxicity will be calculated and monitored with the stopping rules based on 2-stage MiniMax design in the table below. For this early stopping rule, we will only include the rate of unacceptable toxicities from the first infusion. Some patients will receive the second planned DLI. If the rate of unacceptable toxicity for the second DLI exceeds these same boundaries as the first infusion, then the protocol will be amended to delete the plan for the second DLI. Toxicity in the other categories will be informally monitored and tabulated by Type and Grade, but they will not be used to determine tolerability of the procedure.

For purposes of toxicity monitoring, each patient will be followed for an unacceptable toxicity for 8 weeks after each NK cell-enriched DLI. Accrual will not be suspended while collecting data for the interim analyses. However, as soon as a boundary within a stage in the table above is crossed, the study will be closed to further accrual.

Patients will be stratified according to T cell depletion usage or not. Analysis within strata is not planned.

Cohort A (7-8/8 HLA-matched related or unrelated transplantation)

A 2-stage MiniMax design will be used to test the null hypothesis that the unacceptable toxicity rate is ≥ 0.40 against the alternative hypothesis that it is ≤ 0.15 in each arm. Seven patients will be treated in the first stage. If the number of patients with an unacceptable toxicity is equal to 3 or more at 16 weeks after the first NK cell enriched-DLI in one arm, then the study for the arm will be terminated. If there are at most 2 patients (29%) with an unacceptable toxicity at 16 weeks after the first NK cell enriched-DLI, the sample size will be increased up to a maximum of 20 patients. If the number of patients who are alive without relapse/progression is equal to 5 or more at 16 weeks after the first NK cell enriched-DLI, then the study for the arm will be terminated. If there are at most 4 patients (20%) with an unacceptable toxicity at 16 weeks after the first NK cell enriched-DLI, this protocol will be deemed safe and continue to accrue to a total of 25 patients. This design has a significance level of 0.05, a power of 0.80, a probability of early termination under the null of 0.58, and an expected sample size under the null of 12 patients.

Table 6

Stage	Total Accrual	Close study/therapy if number of patients with unacceptable toxicity is \geq
1	7	3 (43%)

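### The 46% and 34% PFS nulls are not adjusted for entry at a first DLI 1-6 months after transplant, so the stated 0.05 is not shown to hold and is probably exceeded under the written rule

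*Combined protocol and SAP*

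**What the plan says.** Section 6.1.2 judges each arm on its own against a fixed rate. In Cohort A a two-stage design "will be used to test the null hypothesis that the progression-free survival rate is" at most "46% against the alternative hypothesis that it is" at least 71%. "Nine patients will be treated in the first stage", and an arm with 4 or fewer event-free patients stops. The final criterion reads "If there are at least 16 patients (64%) who are alive without relapse/progression at 1 year after transplantation", out of 25. Cohort B tests 34% against 59%: 12 patients first, stop at 4 or fewer, effective at 13 or more of 25, on the same clock. Both designs claim a significance level of 0.05 and power of 0.80. Section 6.1.1, by contrast, starts PFS at the first NK cell-enriched DLI.

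Section 6.1.2 names no source for the nulls, but they equal the figures in section 2.3: "Preliminary analysis of 98 patients showed that 1-year progression-free survival for 6/6 HLA-matched related or unrelated donor (n = 69") and for 3-5/6 matched related donors (n = 29) was 46% and 34%. That section describes two regimens, fludarabine with melphalan or with busulfan, both including alemtuzumab.

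Entry to the trial comes later. Section 4.4.1 says "The first NK cell-enriched DLI will be administered between one to six months post-transplant". Section 3.1 also requires ECOG 0-2, at least 2.5% donor engraftment, acute GVHD below grade 2 and expected survival of at least 8 weeks. It sets no conditioning or T-cell-depletion requirement. Section 6.2.2, on toxicity, adds: "Patients will be stratified according to T cell depletion usage or not. Analysis within strata is not planned". Section 2.0 reports "approximately a 10% death rate due to the procedure" in the program's own experience, without saying when those deaths occurred.

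**The concern.** Both arms receive NK-DLI, so no concurrent group shows what enrolled patients would do without it. The efficacy verdict rests wholly on whether 46% and 34% describe such patients. A patient who dies in the weeks after transplant is a failure in a rate counted from transplant, but can never reach a first DLI. If the benchmark contains such deaths and the trial cannot, an inactive infusion starts with an advantage, and an arm could be called effective through selection alone. Nothing in the documents restricts, landmarks or adjusts the historical rate.

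**Working it through.** **Inputs.** Boundaries and nulls from 6.1.2: Cohort A (n1 = 9, r1 = 4, n = 25, r = 15, p0 = 0.46, p1 = 0.71); Cohort B (n1 = 12, r1 = 4, n = 25, r = 12, p0 = 0.34, p1 = 0.59). Entry window from 4.4.1. Procedural death of about 10% from 2.0.

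**Step 1: reproduce the stated figures.** The exact probability of declaring an arm effective at true rate p is

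P(p) = Σ over x = r1+1 to n1 of P[Bin(n1, p) = x] × P[Bin(n − n1, p) ≥ r + 1 − x].

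| | alpha at p0 | power at p1 | early stopping at p0 | expected N at p0 |
|---|---|---|---|---|
| A | 0.0485 | 0.803 | 0.598 | 15.4 |
| B | 0.0456 | 0.802 | 0.612 | 17.0 |

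These agree with the plan (0.05, 0.80, 0.60 and 16; 0.05, 0.80, 0.61 and 17). The arithmetic at the stated nulls is correct. There is little slack: on a grid of 0.001, alpha first passes 0.05 at p = 0.462 (A) and 0.345 (B).

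**Step 2: survivor selection on the transplant clock.** Let e be the fraction of the historical series that died before a first DLI would have been possible. Anyone event-free at 12 months after transplant was alive at that point, so p0 = (1 − e) × q. Hence q = p0/(1 − e) is the no-effect rate among survivors. It is a lower bound if patients with persistent disease enter and are counted afresh from DLI. The documents do not give e, so a range is shown.

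| e (assumed) | q, A | alpha, A | q, B | alpha, B |
|---|---|---|---|---|
| 5% | 0.46/0.95 = 0.484 | 0.078 | 0.34/0.95 = 0.358 | 0.067 |
| 10% | 0.46/0.90 = 0.511 | 0.12 | 0.34/0.90 = 0.378 | 0.10 |
| 20% | 0.46/0.80 = 0.575 | 0.30 | 0.34/0.80 = 0.425 | 0.21 |

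The 10% row treats all procedural deaths in section 2.0 as falling before entry.

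**Step 3: the clock in 6.1.1.** If success means 12 event-free months after a DLI at month t, a Weibull model with shape k gives q = exp{ln(p0) × [((12 + t)/12)^k − (t/12)^k]}.

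- Constant hazard (k = 1): q = p0, and alpha stays at 0.0485 and 0.0456.
- Falling hazard (k = 0.7, assumed), t = 1, 3, 6 months: q = 0.504, 0.541, 0.575 in A, with alpha 0.11, 0.20, 0.30; q = 0.386, 0.426, 0.464 in B, with alpha 0.12, 0.22, 0.34.

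**Step 4: the opposite direction.** If enrolled patients would do 5 points worse than the series (0.41 and 0.29), alpha is 0.015 (A) and 0.012 (B).

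**Step 5: precision of the benchmark.** Treating the rates as simple proportions, the standard errors are √(0.46 × 0.54/69) = 0.060 and √(0.34 × 0.66/29) = 0.088.

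**The case against.** The strongest reply is that inflation has not been demonstrated. Section 2.3 gives neither the time origin of its 1-year PFS nor a statement that the 98 were everyone transplanted. The 10% has no timing, and a first DLI may come as early as month 1. The only dated early-mortality figure is in section 2.2: 5% infectious mortality at 100 days with T-cell-depleted grafts, in another center's review. The 5% row then applies, at 0.078 and 0.067. Enrolment may also run the other way. Section 3.1 admits persistent disease and high relapse risk, section 3.2 excludes good-prognosis patients, and Cohort A takes 7/8 donors while the 46% came from 6/6 matches. All of this stands, and it limits how much can be said about size. It does not justify the nulls. Section 2.3 already calls its own series high-risk, so the opposing effect cannot be assumed to cancel the survivor effect.

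A reader might go further in four ways that the documents do not support:

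- That the 0.05 definitely fails. No landmark PFS is given, so this cannot be shown.
- That it fails on either clock. A DLI clock with constant hazard leaves it intact, and the hazard shape is not given.
- That admitting transplants without T-cell depletion inflates it further. Section 2.2 cites 3-year relapse of 62% against 24% in chronic-phase CML, but also a later comparison with no significant overall difference in long-term relapse or survival. Direction and size are unknown.
- That every enrolled patient is event-free at DLI, which under constant hazard and the transplant clock would give 0.25 (A) and 0.28 (B) for a month-3 DLI. Section 3.1 admits persistent disease, so this condition is not imposed.

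The absence of an untreated arm is a legitimate phase II choice. It makes the benchmark matter more, but is not itself the fault.

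**Conclusion.** The concern holds in a limited form and is a should-fix. The stated 0.05 is correct at 46% and 34%, but it is not shown to apply to patients who reach a first DLI. It is probably exceeded under the rule written in 6.1.2: 0.08 to 0.30 in Cohort A and 0.07 to 0.21 in Cohort B for early death of 5% to 20%. This rests on three assumptions: the historical rate runs from transplant, enrolled patients otherwise resemble the series, and early deaths lie in that range. If 6.1.1 governs instead, the effect depends on the hazard shape and may be nil. The result is a missing justification for the only efficacy benchmark, with a likely direction on one clock and an unknown size.

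**What to change.** 1. Reconcile the PFS origin in 6.1.1 with the assessment time in 6.1.2. No corrected null can be set until this is done.
2. Re-estimate the historical rate in the 98-patient series as a landmark PFS. Include patients alive and, as far as records allow, meeting the section 3.1 entry criteria at 1-6 months after transplant, on the same clock as the endpoint. Give its confidence interval and state whether any of these patients received DLI.
3. Use that rate as the null in 6.1.2 and re-derive the boundaries within 25 per arm. If the current boundaries are kept, restate their alpha and power against the landmark null and qualify any effective verdict accordingly.
4. Report the event-free count with its confidence interval by T-cell-depletion status, descriptively and without a separate subgroup verdict.

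The cost is a re-analysis of the program's own series and a protocol amendment, with no added patients or procedures. The operating characteristics will look less favourable if the landmark rate is higher. The estimate will also be imprecise: at most 69 and 29 patients contribute, and the standard errors of about 6 and 9 points already exceed the 5- and 4-point shifts in the 10% scenario. If the landmark rate comes out near 46% and 34%, the present design is supported.

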2.8 Our Data with This Procedure

We delivered 51 NK cell-enriched DLIs to 30 patients following a 3-6/6 HLA-matched T-cell-depleted nonmyeloablative allogeneic transplantation.⁴³ Eight weeks following transplantation, NK cell-enriched DLI were processed using a CD56+ selecting column with up to 3 fresh infusions allowed. Selection resulted in 96% (SD 8%) purity and 83% (SD 21%) yield in the matched setting and 97% (SD 3%) purity and 77% (SD 24%) yield in the mismatched setting (Table 1). The median number of CD3- CD56+ NK cells infused was 10.6 (SD 7.91) x 10⁶ cells/kg and 9.21 (SD 5.56) x 10⁶ cells/kg in the matched and mismatched setting, respectively. The median number of contaminating CD3+ CD56- T cells infused was 0.53 (SD 1.1) x 10⁶ and 0.27 (SD 0.78) x 10⁶ in the matched and mismatched setting, respectively. Only 1 patient each in the matched (n = 14) or mismatched (n = 16) setting experienced severe aGVHD with little other toxicity attributable to the infusions (Table 2 below). Long-term responders with multiple NK-cell-enriched DLIs and improved T cell phenotypic recovery had improved duration of responses (p = 0.0045) and overall survival (OS) (P = 0.0058). Our 1-step, high-yield process is feasible, and results in high doses of NK cells infused with little toxicity, and NK cell-enriched DLIs result in improved immune recovery and outcomes for some patients. Activation of NK cells in vivo after NK cell-enriched DLIs would be the next promising strategy to enhance immune recovery and anti-tumor activity and obtain better clinical outcomes.

TABLE 1 Cell dose infused post-processing

Donor	Cell Dose (Standard Deviation)	% Purity	% Yield	CD3 ⁺ CD56 ⁻ /kg × 10 ⁵	CD3 ⁺ CD56 ⁺ /kg × 10 ⁶	CD3 ⁻ CD56 ⁺ /kg × 10 ⁶
Matched	Median (SD)	96 (8)	83 (21)	.53 (1.1)	1.94 (2.22)	10.60 (7.91)
Mis Matched	Median (SD)	97 (3)	77 (24)	.27 (.78)	3.67 (2.41)	9.21 (5.56)

Table 2

Toxicities for the matched sibling donors, N=14 (24 total NK cell enhanced infusions); Or mismatched family member donors, N=16 (27 total NK cell enhanced infusions)

(A) aGVHD									
Site [↓] /Grade [→]	HLA Matched N=14 patients; 24 total infusions				HLA Mismatched N=16; 27 total infusions				
	1	2	3	4	1	2	3	4	
Skin	1	1	2	-	3	3	1	-	
Gut	2	-	-	-	2	-	-	1	
Liver	-	1	-	-	-	-	1	-	
Overall	2	3	1	-	4	3	-	1	

(B) Non- GVHD toxicity									
Organ System [↓] /CTC Grade [→]	Matched			Mismatched					
	2	3	4	2	3	4/5			
Cardiac-arrhythmia	1	-	-	2	-	-			
Renal Insufficiency	-	-	-	1	-	-			

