3 ELIGIBILITY CRITERIA

3.1 Inclusion criteria

1. Patients with hematologic diseases who have undergone an allogeneic transplantation, using a 7-8/8 HLA-matched related or unrelated donor or 4-6/8 HLA-matched related donor. This may include patients with a mixed chimeric state or disease persistence or at high risk of relapse (these are patients who do not fit exclusionary principle 3 below).
2. Performance status must be ECOG PS 0, 1, or 2.
3. Donor cellular engraftment of at least 2.5%.
4. < Grade 2 acute GVHD at time of the first NK cell-enriched DLI. Patients with treated acute GVHD must be on a stable dose of therapy (no increase in immunosuppressive therapy for the 2 weeks before planned NK cell-enriched DLIs). The dosage/level of immunosuppressive therapy at the time of NK-DLIs should be no greater than 20mg of prednisone daily or mycophenolate 500 mg bid daily or cyclosporine with a target level of 200 ng/mL or tacrolimus with a target level of 10 ng/ml.
5. Estimated survival of at least 8 weeks.
6. Age of \geq 18 years.
7. Females of childbearing potential should have a negative serum beta-HCG test within 48 hours of beginning DLI and/or DUK-CPG-01 unless contraception is used after initial testing. *A female of childbearing potential (FCBP) is a sexually mature female who: 1) has not undergone a hysterectomy or bilateral oophorectomy; or 2) has not been naturally postmenopausal for at least 24 consecutive months (i.e., has had menses at any time in the preceding 24 consecutive months).*

8. Males must agree to use a medically acceptable form of birth control in order to be in this study and for 3 months after infusion

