6.1.1 Definition of progression-free survival

Progression-free survival is defined from the day of the first NK cell-enriched DLI until the day of disease relapse, disease progression, or death whichever comes first. Patient without relapse, progression, or death will be censored at the last follow-up.

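### Section 6.1.1 starts PFS at the first DLI, but every decision sentence in 6.1.2 counts from transplantation, so the go/no-go rule does not test one-year PFS as defined

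*Combined protocol and SAP*

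**What the plan says.** Section 6.1.1 gives the only definition of the endpoint: "Progression-free survival is defined from the day of the first NK cell-enriched DLI until the day of disease relapse", with progression and death as the other events.

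Section 6.1.2 states a two-stage minimax rule for each arm, with four decision sentences per cohort. All eight count event-free patients at one year after transplantation. The final rule is "If there are at least 16 patients (64%) who are alive without relapse/progression at 1 year after transplantation, this protocol will be deemed effective" in Cohort A and "If there are at least 13 patients (52%) who are alive without relapse/progression at 1 year after transplantation, this protocol will be deemed effective" in Cohort B. The hypotheses in 6.1.2 and Tables 4 and 5 give no time point, and the objectives say one-year PFS without an origin.

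The two origins differ by design. Section 4.4.1 says: "The first NK cell-enriched DLI will be administered between one to six months post-transplant".

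The nulls of 46% and 34% match the program's own series in Section 2.3: "Preliminary analysis of 98 patients showed that 1-year progression-free survival for 6/6 HLA-matched related or unrelated donor (n = 69") was 46%, and 34% in the 29 patients with 3-5/6 matched related donors. That section does not say when the year began.

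Section 4.3.2 times the required post-treatment disease assessments at 3, 6 and 12 months after the last DLI. On the second infusion, 4.4.1 says: "The second NK cell-enriched DLI will be administered one to three months post the first infusion".

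**The concern.** A patient infused at month 3 who progresses at month 13 after transplantation is a success under 6.1.2. Under 6.1.1 the same patient has an event at month 10. Nothing in the protocol says which reading governs, and the verdict for each arm turns on a single patient: 16 against 15 in Cohort A, 13 against 12 in Cohort B. Two analysts, one following each section, could reach opposite conclusions from the same data.

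The operating characteristics are exposed as well. They hold only if 46% and 34% are the null probabilities of success at the time point counted. The protocol does not say which clock those rates describe, or whether the series resembles patients who go on to receive a DLI.

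**Working it through.** **Inputs.** Boundaries (first stage, final) from 6.1.2: 4/9 and 15/25 in Cohort A; 4/12 and 12/25 in Cohort B. Null and target rates: 0.46 and 0.71 (A); 0.34 and 0.59 (B). First DLI at months 1 to 6 (4.4.1). Pilot timing from 2.8: "Eight weeks following transplantation, NK cell-enriched DLI were processed using a CD56+ selecting column with up to 3 fresh infusions allowed".

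**Step 1: the plan's own figures.** The chance of declaring an arm effective when each patient succeeds with probability p is

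R(p) = Σ over x from r1+1 to n1 of P{Bin(n1, p) = x} × P{Bin(n − n1, p) ≥ r + 1 − x}.

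- Cohort A: R(0.46) = 0.0485, R(0.71) = 0.803, early termination 0.598, expected size 15.4.
- Cohort B: R(0.34) = 0.0456, R(0.59) = 0.802, early termination 0.612, expected size 17.0.

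These agree with the stated 0.05 and 0.80, with 0.60 and 0.61, and (to within one patient) with 16 and 17. A search for the minimax design returns the same boundaries.

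**Step 2: what the written rule covers.** At one year after transplantation a patient infused at month t has 12 − t months of PFS as defined: 11 months at t = 1 and 6 at t = 6.

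**Step 3: size of the mismatch (illustration).** Assume entrants are event-free at DLI and the hazard is constant afterwards. If true one-year PFS from DLI is q, the written rule sees p = q^((12 − t)/12). Eight weeks is 56 days, so t = 1.84 and the exponent is 10.16/12 = 0.847.

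| | q | p | 25 × (p − q) | R(q) | R(p) | R(p) − R(q) |
|---|---|---|---|---|---|---|
| A, null | 0.46 | 0.518 | 1.5 | 0.0485 | 0.1393 | 0.091 |
| B, null | 0.34 | 0.401 | 1.5 | 0.0456 | 0.1485 | 0.103 |
| A, target | 0.71 | 0.748 | 1.0 | 0.803 | 0.897 | 0.094 |
| B, target | 0.59 | 0.640 | 1.2 | 0.802 | 0.912 | 0.110 |

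The fourth column is the expected number of patients per 25 who succeed under the rule but have an event within a year of DLI. Under these assumptions every success on the DLI clock is also one on the transplant clock, so the last column is the chance of opposite verdicts. Its maximum over q is 0.195 in A (q = 0.589) and 0.226 in B (q = 0.466).

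**Step 4: alpha of the written rule if 46% and 34% apply from DLI.** Same assumptions, Cohort A/B:

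- month 1: p = 0.491/0.372, alpha 0.088/0.089
- 8 weeks: p = 0.518/0.401, alpha 0.14/0.15
- month 3: p = 0.559/0.445, alpha 0.246/0.276

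In the other direction, a true null 5 points lower at 8 weeks gives 0.060/0.058, and 10 points lower gives 0.020/0.016.

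**Step 5: alpha after moving the count to the DLI clock.** With the boundaries unchanged, alpha is 0.0485/0.0456 if the nulls hold on that clock. It is 0.025/0.022 if the true nulls are 3 points lower and 0.087/0.086 if they are 3 points higher.

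**The case against.** The transplant clock may have been intended, to match the historical series. That would not remove the conflict: 6.1.1 would then have to change, and the null would need to allow for entrants having come through the interval before DLI. If the rates run from transplantation, entrants are event-free at DLI and the hazard is constant, the relevant null is S(12)/S(t), which equals p in Step 4, so the same alphas result. Nor is this easily read as a slip. The wording recurs eight times in the operative rule, while the toxicity rules in 6.2.2 count from the first DLI.

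It can also be said that the sizes rest on assumptions. That stands. Section 3.1 does not require entrants to be event-free: "This may include patients with a mixed chimeric state or disease persistence or at high risk of relapse". A patient who relapsed before DLI could fail on the transplant clock without having an event on the DLI clock. Exclusion criterion 3 removes good-risk patients, which could put the true null below the historical rate. The contradiction itself needs no assumption.

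On visit timing, a reader might infer that a progression first found at the last 12-month visit cannot be dated before or after one year from the first DLI. The documents do not support that. PFS ends on the day of progression, and 4.3.2 allows earlier restaging when progression is suspected. The note in 4.3.3 on single-DLI patients and Appendix V footnote 3 point to three-monthly follow-up or restaging. Single-DLI patients fit the 6.1.1 clock exactly. What remains is ordinary interval censoring in two-DLI patients.

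**Conclusion.** The point holds and should be corrected before the rule is applied. As written, 6.1.2 does not test the endpoint defined in 6.1.1, and the stated alpha and power are not assured for it. The fault is the clock and not the arithmetic.

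At pilot timing the mismatch is about one to one and a half patients per 25. That is enough to reverse an arm's verdict in roughly one trial in ten at the null or target rates, and in about one in five at worst. These sizes depend on entrants being event-free at DLI, a constant hazard and a common infusion time of 8 weeks.

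A reader might infer that the true type I error is inflated to about 0.14 or 0.15. The documents do not establish this. They do not give the distribution of DLI times, the hazard shape, the disease status of entrants at DLI or the origin of the nulls, and plausible departures move alpha to either side of 0.05.

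**What to change.** 1. **One time origin.** In all eight decision sentences of 6.1.2, change the time point to one year after the first NK cell-enriched DLI, and keep the boundaries. This is a wording amendment. Its cost is that each stage decision comes later by the transplant-to-DLI interval: one to six months, or about 8 weeks at pilot timing.

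2. **Origin of the nulls.** State the time origin and population of the 46% and 34% figures in 2.3. If they run from transplantation, say that alpha 0.05 and power 0.80 are conditional on the same rates holding from the first DLI, and report alpha over a stated range of nulls, as in Step 5. This costs a paragraph and a small table. Item 1 alone removes the contradiction but does not secure 0.05.

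3. **Twelve-month status (smaller, separate point).** With the second DLI one to three months after the first, the 12-month assessment in 4.3.2 nominally falls 13 to 15 months after the first DLI. State how status at 12 months from the first DLI is determined in these patients, for example by a rule for dating progression. Reconcile 4.3.2 with the note in 4.3.3 and Appendix V footnote 3, which give different follow-up intervals. A dating rule needs no extra visit.
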